2.6.1 Phase I Study of CPX-351: CLTR0305-101

[figure not shown]
The primary goal for this study was to establish the MTD for CPX-351 and recommend a dose for further study in a Phase II setting. Pharmacokinetics was assessed at every dose level and patients were monitored for signs of antileukemic activity.

The dosage regimen was designed to mimic the 7-day drug exposure provided by conventional 7+3 treatment. A single induction course administers doses on Days 1, 3, and 5, by 90 minute infusion. Patients with AML (multiply relapsed, refractory, or with first CR duration of 6 months or less), ALL, and high risk MDS were eligible.

Dose limiting toxicities were observed at the 10th dose level: 134 u/m² (134 mg/m² cytarabine + 59 mg/m² daunorubicin). One patient had significant reduction in post treatment LVEF and as a result both Phase II studies included a cap (500 mg/m²) on cumulative anthracycline dose after one induction course of CPX-351 and patients with significant pre-existing cardiac disease were excluded. Other dose-limiting toxicities included hypertensive crisis and prolonged (>56 days) cytopenias.

The Phase I study of CPX-351 assessed the concentrations of cytarabine, daunorubicin, uracil arabinoside, and daunorubicinol at multiple dose levels and found that they exhibited mono-exponential, first order elimination with minimal early phase distribution. (Figure 1)

Figure 1: CPX-351 Day 1 and 5 Pharmacokinetics from Protocol CLTR0305-101

The day 1 (single dose) and day 5 (multiple dose) C_{max} and $AUC_{(0-\tau)}$ were linear and the 5:1 molar ratio of cytarabine to daunorubicin was maintained for up to 24 hours at all dose levels on days 1 and 5.

The pharmacokinetic analysis confirmed higher absolute plasma concentrations of both drugs compared to that expected with the conventional 7+3 regimen with a markedly prolonged mean half-life for both cytarabine and daunorubicin and greater drug exposure (AUC). Measurable drug levels were present seven days after the last infusion of CPX-351 (Study Day 12). Compared to infusions of the conventional drugs, CPX-351 administration was associated with substantially greater AUC and half-lives for plasma cytarabine and daunorubicin.(13) (Table 2)

Table 2: Cytarabine and Daunorubicin Pharmacokinetics following CPX-351 (101 u/m², Day 5)

Variable	C _{max} (ng/mL)	T _{max} (hr)	AUC _(0-τ) (ng*hr/mL)	T _{1/2} (hr)	CL (mL/hr/m ²)
Cytarabine					
N	13	13	13	13	13
Median	55,800	2	1,487,638	31.1	67.9

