3.3 Exploratory Objectives

To investigate the effect of CPX-351 on immune response, as determined by the effect on recovery of functional pathogen-specific and leukemia-specific immune responses and the recovery and function of NK cells.

To investigate the role of Troponin-T as an early marker for CPX-351-induced cardiotoxicity.

To investigate ex vivo the cytotoxicity of combination of Pim kinase inhibitor(s) and CPX-351 on circulating leukemia cells.

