6.1 Pre-Treatment Evaluations

The date of the first test or exam will be considered as date of the screening visit.

Procedure	Evaluation	Timing
Informed Consent	It should be personally signed and dated by the patient. The investigator must also personally sign and date the document. A copy of the Informed Consent must be given to the patient. The patient's study screening must be conspicuously noted in the source documentation.	Informed consent should be obtained prior to initiation of screening procedures. If the period between ICF signature date and screening visit is ≥ 30 days the patient must sign another ICF.
Demography	Date of birth, sex Basis for high risk of induction mortality	Within 14 days prior to registration in core
Medical History	Complete medical history	Within 14 days prior to registration in core
Physical Exam	Objective review of body systems ECOG Performance Status	Within 3 days prior to registration in core
Vital Signs	Heart rate Blood pressure Temperature Respiratory rate	Within 3 days prior to registration in core
Hematology	Hemoglobin White Blood Count Platelets Differential Count (may be omitted if WBC $\leq 0.5 \times 10^9/L$)	Within 1 day prior to registration in core
Biochemistry	BUN Creatinine Electrolytes (Sodium, Potassium, Chloride) Bilirubin AST or ALT	Within 1 day prior to registration in core
Bone Marrow Aspiration and/or Biopsy	Morphology	Within 14 days prior to registration in core
Copper levels	Serum copper	Within 14 days prior to registration in core

Procedure	Evaluation	Timing
Diagnostic Imaging	Chest X-ray Echocardiography or MUGA scan	Within 28 days prior to registration in core
ECG		Within 14 days prior to registration in core
Cytogenetics	Cytogenetics (performed locally) Molecular abnormalities: Evaluation of CEBPA, FLT3, and NPM1	Within 3 months prior to registration in core: patients may be registered and treated prior to the cytogenetic test results; however, every attempt should be made to have the results prior to registration in core
Correlative studies (optional)*	Immune reconstitution	Before the start of induction therapy
Correlative studies (optional)*	BNP, Troponin I, high-sensitivity troponin (I or T)	Before the start of induction chemotherapy
Correlative studies (optional)*	Pharmacodynamics	Before the start of induction chemotherapy
Pregnancy Test	Urine or serum pregnancy test	Within 7 days prior to registration in core

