10.0 Statistical Considerations(16, 17)

General Description:

This is a Phase II study of CPX-351 Liposome Injection in newly diagnosed AML patients with high risk of induction mortality. Two dose levels (50 units/m² and 75 units/m²) of CPX-351 will be studied initially. The primary objective is to evaluate treatment response. The efficacy outcome is CR or CRi within two induction cycles. A maximum of 30 patients will be equally randomized to the two dose levels. A Bayesian method by Thall et al (1995)

will be used for futility and toxicity monitoring. After 15 patients have been accrued to each dose level, an assessment of overall safety/dose limiting toxicities and efficacy will be made and one dose level will be chosen for further study. OR if both dose levels are safe and further dose escalation seems possible, one additional cohort with a dose of 100 units/m² will be open. A maximum of 15 patients will be enrolled in this arm and the same toxicity and futility monitor rules will be applied. After 2 or 3 dose levels have been studied, one dose levels will be chosen for further study. An expansion cohort of 10 patients will be treated at the dose level with a favorable response and/or toxicity profile for further evaluation for safety and efficacy. Consequently, the preferred dose level has 25 patients evaluable.

Additional 25 patients will be added to the arm with the dose of 100 units/m², the sample size for this arm will be up to 40, and the maximum number of patients for all three arms will be up to 80.

Multc Lean software version 2.1 developed in the Department of Biostatistics MDACC was used for the study design.

The study will monitor futility and toxicity, and the monitoring rules will be applied to each dose separately. If study in one of the two doses is stopped early due to futility or excessive toxicity, all the future patients will be enrolled in the open dose arm (i.e., without randomization). In the case the lower dose (50 units/m²) has been shown to be too toxic at an interim look (thus stop further patient enrollment) the higher dose (75 units/m²) will also stop accrual.

Futility monitoring:

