Data analysis will be performed using SAS or S-plus, as appropriate. For each arm, the CR/CR_i rate and the DLT rate will be estimated with 95% confidence intervals. The intent-to-treat patients will be used for the primary efficacy analysis, patients who lost-to-follow up in the first 2 cycles will be treated as failures. Patients who received at least one dose of the treatment drug will be evaluable for toxicity outcomes. In addition, Fisher's exact test will be used to compare the response rate and toxicity rate between the two dose levels. For the exploratory objectives, Fisher's exact test will be used to compare immune responses between different doses of CPX-351. Two-sample t test or ANOVA or Fisher's exact test will be used to check the association between Troponin - T and cardiotoxicity, and t test or ANOVA will be used to compare the apoptosis of ex-vivo cultured leukemia cells.

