Both cTnT and cTnI have been demonstrated in multiple clinical studies to be sensitive and specific markers for detecting myocardial injury after chemotherapy administration. The level of troponin released into circulation has a good predictive value for subsequent decrease in LV ejection fraction and adverse cardiac events long before the impairment is observed by echocardiogram or symptoms have developed. Elevation in troponin has shown a positive predictive value of 50-84%, and a negative predictive value of 90-99%.^{5, 7} Furthermore, the peak value and the duration of elevated troponin level have a strong relationship with the degree of LV dysfunction. In contrast, BNP, NT-proBNP, CK, CK-MB and CRP have shown to be less sensitive and specific in detecting subclinical heart failure in this group of patients.^{8, 9}

Recent advances in assay technology have led to more sensitive and precise cardiac troponin T assays that can detect TnT level as low as 0.005 µg per liter.¹⁰ With increasing in sensitivity, high-sensitive troponin T (hs-TnT) has superiority over standard troponin test in early diagnosis of acute myocardial infarction.¹¹ In chronic stable angina, higher levels of hs-TnT has been shown to be associated with the higher incidence of cardiovascular death and heart failure in the future.¹² Recently, hs-TnT has been evaluated as a peri-operative risk stratification in non-cardiac surgery patients.¹³ Interestingly, they found that hs-TnT level above universal cut-off were associated with a 2.6-fold increase in in-hospital mortality and morbidities from cardiovascular system.

To our knowledge, no prior study has ever evaluated hs-TnT during CPX-351 chemotherapy administration. Therefore, our primary objective is to assess whether hs-TnT obtained during the course of CPX-351 chemotherapy could allow us to monitor the development of acute cardiotoxicity.

- Primary objective:

To test the feasibility of using high-sensitivity troponin T to monitor acute CPX-351-induced cardiotoxicity. In addition, BNP and cardiac troponin I will be measured.

- Roche high sensitivity troponin T assay is a sandwich chemiluminescent assay. High sensitivity troponin T assay gives detection limit of 5 ng/L and the 99th percentile of cutoff 14 ng/L. It can be run on MODULAR ANALYTICS E170, Elecsys 2010, cobas e411, cobas e 601 and cobas e 602 analyzers.

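### The troponin analysis relates an undefined cardiotoxicity outcome to troponin T by group-comparison tests only; events may be too few for this, and the LVEF values already scheduled are not used as a continuous outcome.

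*Combined protocol and SAP*

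**What the plan says.** Section 3.3 lists an exploratory objective: "To investigate the role of Troponin-T as an early marker for CPX-351-induced cardiotoxicity". Appendix 7 states its aim as feasibility: "To test the feasibility of using high-sensitivity troponin T to monitor acute CPX-351-induced cardiotoxicity".

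The analysis is one clause in section 10.0, under Statistical methods: a t test, ANOVA or Fisher's exact test "will be used to check the association between Troponin - T and cardiotoxicity". It does not say what counts as cardiotoxicity, which troponin value is used (peak, change or cut-off), which variable forms the groups, or what is done if there are no events.

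Two LVEF thresholds elsewhere could define an event. Section 9.3 records any LVEF below 50% as an adverse event. Section 4.0 counts a drug-related fall of Grade 3 or higher as dose limiting.

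The data are already scheduled. Sections 6.1 and 6.3 call for an echocardiogram or MUGA at baseline and after treatment ends. Appendix 7 schedules troponin before each cycle, about a day after the Day 1 and Day 5 doses, around Day 14, and at end of treatment. Sampling is optional.

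On the assay, section 3.3 and Appendix 7 specify troponin T. The visit tables in 6.1, 6.2 and 6.3 list "BNP, Troponin I, high-sensitivity troponin (I or T"), which a sample without a high-sensitivity T result would satisfy.

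**The concern.** A comparison of patients with and without an event is only as informative as its smaller group. The nearest evidence in the documents suggests that group could be very small or empty, and section 10.0 offers no other analysis.

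The outcome is also open. LVEF below 50% would capture more patients than Grade 3 or higher, so the choice of definition determines the event count and should not wait until the data are seen.

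The objective concerns an early marker, yet nothing in section 10.0 requires the troponin value to precede the LVEF reading.

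At stake is whether the samples yield a usable estimate. No primary or secondary conclusion of the trial is affected.

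**Working it through.** The plan gives no event count, effect size or power for this analysis, so there is no figure of its own to reproduce. Two-sided alpha of 0.05 is assumed throughout.

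**Inputs**
- Maximum sample: section 10.0 says "the maximum number of patients for all three arms will be up to 80" (15 + 25 + 40 = 80).
- Cardiac count: section 2.6.1 reports "One patient had significant reduction in post treatment LVEF", in a study of 48 patients. It follows the statement "Dose limiting toxicities were observed at the 10th dose level", which was 134 u/m²; this trial's induction arms are 50, 75 and 100 u/m².
- Study 204 (section 2.6.2): no surplus of cardiac events over 7+3, but no count.
- Number sampled: not stated; 40 to 80 is assumed because collection is optional.

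**Expected events, assuming a rate of 1/48**
- N = 80: 80 × 1/48 = 1.67. P(none) = (47/48)^80 = 0.19. P(1 or 2) = 0.58. P(3 or more) = 0.23.
- N = 40: 40 × 1/48 = 0.83. P(none) = (47/48)^40 = 0.43.
- The exact 95% interval for 1/48 is 0.05% to 11.1%, so the expected count in 80 runs from 0.04 to 8.9.

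**t-test power, 80 patients grouped by event**, from the noncentral t with noncentrality d / √(1/n₁ + 1/n₂):

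| Events vs none | Power at 1 SD | Difference for 80% power |
|---|---|---|
| 1 vs 79 | 17% | 2.9 SD |
| 2 vs 78 | 28% | 2.0 SD |
| 4 vs 76 (assumed 5% rate) | 49% | 1.5 SD |
| 8 vs 72 (assumed 10% rate) | 76% | 1.1 SD |

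**Fisher's test, best case (every event troponin-positive), N = 80, k positive**
- One event: p = k/80, so p ≤ 0.05 needs k ≤ 4.
- Two events: p = k(k−1)/(80×79). For k = 18 this is 306/6320 = 0.048; for k = 19 it is 342/6320 = 0.054. So k ≤ 18 is needed.

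**Continuous LVEF change.** The correlation detectable with 80% power is r = tanh[(1.96 + 0.84)/√(n−3)]: 0.31 for n = 80, 0.37 for n = 56, 0.43 for n = 40.

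**How many pairs are realistic.** Section 3.1 targets patients with a 30–50% predicted risk of death by Day 60. At that prediction, 80 × 0.70 = 56 to 80 × 0.50 = 40 patients would be alive at Day 60. Some who die early may have had a follow-up echo, and some survivors will lack troponin samples, so these are rough figures. Eighty pairs are unlikely.

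**The case against.** A reader might infer that the trial's own event rate implies one or two events, leaving the planned tests almost nothing to compare. The documents do not support that, for three reasons.

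- No rate is stated, and Appendix 7 says CPX-351 cardiotoxicity has not been evaluated. The 1/48 joins one fall, described among toxicities at 134 u/m², to a denominator covering all dose levels. Lower induction doses and the LVEF entry requirement could lower the rate; this population, repeated consolidation or a looser definition could raise it. The predictive values cited in Appendix 7 for chemotherapy generally (PPV 50–84%, NPV 90–99%) would, if 10% of 80 patients were positive (an assumption), imply between 8×0.50 + 72×0.01 = 4.7 and 8×0.84 + 72×0.10 = 13.9 events.
- Section 10.0 does not say that patients are grouped by cardiotoxicity. Appendix 7 gives a 14 ng/L cut-off, so LVEF could be compared between troponin groups, and the power table would not apply.
- Fisher's test can work with two events. At a rate of 1/48, with 90% sensitivity and specificity assumed, simulation puts its power near 46% with 80 patients and 16% with 40.

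All three stand. It is also fair that the objective is exploratory and framed as feasibility, so no power is owed.

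The schedule partly meets the timing point. Section 6.2 triggers repeat LVEF between courses only above 300 mg/m² cumulative daunorubicin. At 0.44 mg per unit and with no earlier anthracycline, the 100 u/m² arm reaches 132 + 88 = 220 mg/m² after two inductions, 277 after one consolidation and 334 after two. Most troponin samples will therefore precede the LVEF reading, although the analysis does not require it.

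Nothing in the plan proposes pooling troponin I and T; the assay point is a reconciliation of wording. None of this supplies the missing definition or a method for few or no events.

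**Conclusion.** The concern holds as a minor, correctable gap. The outcome and the troponin measure are undefined, and group comparison is the only method, although it may have few or no events to work with. On the assumed 1/48, about 1.7 events are expected in 80, with limits so wide (about 0 to 9) that no particular count should be predicted. At 2 to 4 events a t test has 28–49% power for a 1 SD difference; with none, no comparison can be made.

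A continuous LVEF-change analysis does not depend on the event count, but its advantage should not be overstated. The detectable correlation of 0.31 needs 80 pairs; about 0.43, from 40 pairs, is a safer planning figure. Patients without a follow-up LVEF may differ systematically from those with one.

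**What to change.** In section 10.0, replace the troponin clause with text that does the following:

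- Makes the main analysis an estimate with 95% confidence interval (Spearman correlation or regression) of LVEF change, baseline to end-of-treatment echo/MUGA, on peak high-sensitivity troponin T from first-induction samples up to Day 14. Adjust for baseline LVEF and cumulative CPX-351 exposure. Treat values below the 5 ng/L detection limit as censored.
- Uses only troponin drawn before the LVEF reading.
- States which LVEF threshold defines cardiotoxicity and reports that yes/no comparison descriptively, giving the expected event range as an assumption.
- Reports how many patients lack end-of-treatment LVEF and why, including early death, and notes that this missingness may be informative.

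Reconcile the I-or-T wording in sections 6.1, 6.2 and 6.3 with the troponin T specified in section 3.3 and Appendix 7.

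The cost is a few lines of text, with no new samples or visits. The downside is that the LVEF-change result describes only patients who have a follow-up echo or MUGA.

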12.0 APPENDIX 1: Patient Evaluation Flow Sheet – Treatment Phase

Evaluations (except screening) to be conducted for each INDUCTION¹ and CONSOLIDATION:

Day:	Screening	1 ±2	2 ±2	3 ±2	4 ±2	5 ±2	6 ±2	7 ±2	10 ±2	14 ±3	21 ±3	28 ±3	35 ±3	42 ±3	Weekly ³ ±3	End of Phase/Early Termination
Informed Consent ⁴	x															
Medical History	x															
Physical Exam	x								x				x			x
Vital Signs	x								x				x			x
ECOG Performance Status	x															x
ECG	x															x
Registration	x															
Hematology	x	x		x		x		x	x	x	x	x	x	x	x	x
Biochemistry	x	x		x		x		x	x	x	x	x	x	x		x
Pregnancy Test ⁹	x															
Copper levels	x									x ⁸						x
Bone Marrow Aspiration/Biopsy	x									x ⁵						
Chest X-ray	x															
Echocardiography/MUGA	x	x ¹⁰										x				x
Response Assessment											x ⁶					
Cytogenetics/Molecular Markers	x									x						
Adverse Events																x
Concomitant Medications																x
CPX-351 Administration	x		x		x ²											
Immune markers*	x	x ⁷														
Cardiac markers*	x	x	x			x			x							x
Pharmacodynamics*	x	x	x													

*Optional

¹The first induction may end prematurely if a second induction is necessary, see Section 0. The schedule of evaluations for the first induction is followed until the second induction starts, then the evaluations are followed as indicated in the flow sheet, beginning with Day 1

² Second inductions and consolidations of are CPX-351 on Days 1 and 3, see Section 4.6

³Continue weekly evaluations until confirmation of response (CR/CRi) or persistent disease is declared

⁴Within 30 days prior to start of screening, if informed consent was collected, 30 days elapse and the patient is still not screened he/she must sign another ICF

⁵Required after each induction; (in case the Day 28 (+/-7 days) bone marrow is non-evaluable or assessment of aplasia is equivocal, a repeat evaluation may be performed 5-10 days later, at the discretion of the treating physician, in order to determine effect and need for second induction); as needed thereafter to confirm response/persistence/relapse in second inductions & consolidations

⁶Induction(s) only; see Section 8.4.1 for details on when response is assessed.

⁷At start of induction, induction 2 (when applicable), each consolidation

13.0 APPENDIX 2: Patient Evaluation Flow Sheet –Follow-up

	Monthly for 1 Year (± 10 Days)	Every 2-3 months for 1 year	Every 3-4 months for 1 year	Early Termination
Patient status report	X ¹			x
Hematology		x		x
Biochemistry		x		
Copper levels	only if abnormal ²			
Bone Marrow Aspiration/Biopsy			
x
 
For patients in CR, consider performing if peripheral blood counts fall below 1000/μL for ANC or 100,000/μL for platelets for >1 month with no obvious explanation for the drop or at any time there is suspicion of relapse; for patients in CRI perform if counts fall significantly below peak recovery. If the peripheral blood counts in a patient with a CRI recover to CR levels ($\geq 1000/\mu$L for ANC or $\geq 100,000/\mu$L for platelets), consider performing a bone marrow evaluation to confirm full CR. Following the first year of follow up, aspirations will be done as clinically indicated; record relapse information, including any bone marrow evaluations. Not required following the initiation of new therapy and or relapse.
	
Echocardiography or MUGA scan			
x
 
Perform every 3-4 months if last Treatment Phase LVEF was reduced >10% from baseline and is less than 50%. Continue assessments until LVEF returns to baseline or until 1 year from start of therapy.
	

¹ Survival followed until death

²>20% above upper limit of normal. To be performed monthly until return to within 20% of ULN, or until 1 year from the last dose, or the initiation of new therapy, or relapse (whichever is earlier).

14.0 APPENDIX 4: Performance Status – ECOG

Grade	Description
0	Fully active, able to carry on all pre-disease performance without restriction (Karnofsky 90-100)
1	Restricted in physically strenuous activity but ambulatory and able to carry out work of a light or sedentary nature (e.g., light housework, office work) (Karnofsky 70-80).
2	Ambulatory and capable of all self-care but unable to carry out any work activities. Up and about more than 50% of waking hours (Karnofsky 50-60).
3	Capable of only limited self-care, confined to bed or chair more than 50% of waking hours (Karnofsky 30-40).
4	Completely disabled. Cannot carry on any self-care. Totally confined to bed or chair (Karnofsky 10-20).

15.0 APPENDIX 5: Common Terminology Criteria for Adverse Events V4.0 (CTCAE)

This 80 page document can be obtained as a pdf file from <http://ctep.cancer.gov>.
The publication date is May 28, 2009

